Group PT and STRIDE will randomize sites 1:1 to foundational REP or enREP, which consists of adding higher intensity implementation support for VAMCs that do not meet adoption goals at 6 months nor sustainment goals at months 8 and 9 (for STRIDE and GPT, respectively). The Caregiver FIRST design is slightly different to take advantage of the fact that CSP requested national implementation to address unmet needs for training and to support the expansion of general caregiver services required by the MISSION Act. Following Caregiver FIRST roll-out at all 150 medical centers, we will enroll a subset of sites that did not meet a priori adoption benchmarks at 6 months (n=24) and randomize them 1:1 to continue foundational REP or receive higher intensity implementation support. A run-in design is critical for this project for efficient use of resources because we cannot forecast which sites will be able to launch the mandatory EBP independently and which will need a more intensive approach to adopt the EBP. All projects use a common set of foundational REP activities and higher intensity strategies. Primary outcomes will be assessed at project specific time points between 10-18 months from the beginning of foundational REP, based on previous experience of how long it takes to implement each EBP.

[figure not shown]

Figure 3. Function QUERI Project Design Overview

Implementation Project 1: Group PT for Knee OA

Urgency of improving functional outcomes in Veterans with knee OA and relationship to ICF. Knee OA is a common and often disabling health condition that affects 14 million people in

Objective	Improve access to PT to Veterans with knee osteoarthritis by delivering PT in a group setting
Evidence	Allen et al. Group Versus Individual Physical Therapy for Veterans With Knee Osteoarthritis: Randomized Clinical Trial. Phys Ther 2016, 96:597-608.
Primary Partners	VA Physical Medicine & Rehabilitation Program

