Following announcement by the National Director of CSP of Caregivers FIRST national roll-out to all 150 VAMCs as a mandatory new program, all sites (n=150) will receive foundational REP for 6 months. In the CRT to address Aim 2 we will enroll up to 25 sites that did not meet adoption benchmarks (i.e. did not deliver a round of Caregivers FIRST in first 6-months or had low enrollment defined as 4 or less caregivers trained in the first 6-months). Based on the Roger's diffusion model, 87 we anticipate approximately 23% of sites will launch Caregivers FIRST within the first 6 months after national implementation is announced, with the remaining sites nonresponsive during this initial 6-month time period. A subset of the nonresponding sites (n=85) will be enrolled and randomized (up to n=25) to either continue foundational REP or receive higher intensity support strategies. To select the subset of sites to approach initially for enrollment and subsequent randomization, the non-responding sites will be prioritized by VISN, site complexity level, implementation activity (e.g., no implementation versus implementing but with low enrollment), and CSP staffing capacity (CSP total staffing FY20). The goal will be to select from nonresponding sites distributed across VISNs (approximately 2 per VISN if there are eligible sites) with sites systematically selected to approach for enrollment based on complexity level and lowest implementation activity within a VISN. In partnership with CSP, we will invite all CSP VISN Leads to encourage medical centers within their region to enroll. Once sites are enrolled a stratified, randomization will be conducted with site complexity level as 2 dichotomous stratification variables: 1) low complexity (2, 3 and no complexity) versus all others and 2) prior implementation of Caregivers FIRST (implementation in FY21 or FY22 vs. none). Additional site inclusion criteria include: (1) VISN lead and CSP champion willing to participate in study, willing to document class participation, and participate in assessments; (2) agree to start program within 6 months. We anticipate that the vast majority of non-adopting sites will agree to try to start a program because the announcement of Caregiver FIRST as a mandatory program provides strong incentives for them to be successful.

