Outcomes. Implementation outcomes. Adoption is a cluster-level dichotomous outcome defined as meeting a threshold of four or more training classes delivered to a minimum of five caregivers over a cumulative 12-month period (yes) or not meeting this threshold is considered non-adoption (no). In addition, while 12 months is the primary endpoint, penetration and fidelity outcomes will also be assessed over 6- and 18-month time periods with descriptive results. Penetration (primary outcome) defined as the (1) proportion of caregivers who received consults for VA caregiver education and training services who attended at least one class at a medical center over a 12-month period and (2) the number of classes delivered over a 12-month period. Fidelity outcomes are cluster-level defined as (1) the proportion of the number of recommended classes delivered over a 12-month period, (2) the number of caregivers who attended at least one class over a 12-month period, and (3) the mean number of classes attended per caregiver over a 12-month period. Effectiveness outcomes/ Quality metrics. Effectiveness outcomes will include Veteran days in the community (e.g., not in a hospital or nursing home) over a 6 month period after caregiver participation in Caregivers FIRST. We will use the inclusion of Caregivers FIRST in VA medical center performance plans as the quality metric, where sites report the status on meeting requirements within the CSP Program of General Caregiver Support Services (PGCSS). In addition, we will evaluate the number of caregivers enrolled with each site's PGCSS and whether the quality metrics change based on the implementation approach.

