Analyses. To address the question: Are there differences in implementation outcomes (penetration, fidelity) at 6, 12, or 18 months between arms? We hypothesize that sites randomized to higher intensity strategies will achieve higher penetration and fidelity. As part of our type III effectiveness-implementation hybrid design framework, the primary research question compares differences in implementation outcomes (penetration, fidelity, and adoption) between implementation arms at 12 months. Implementation outcomes are continuous, count, and binary outcomes, and generalized linear models⁷⁵ will be used to examine the effect of high-touch support on implementation outcomes at 12 months. The main predictor of interest will be enhanced (high touch) implementation support vs. foundational (low touch) implementation support, and stratification variables for site complexity (low complexity (2, 3, and no complexity) versus all others) and prior implementation of Caregivers FIRST or not will be included; other facility level covariates for consideration are CSP program quality score and size of CSP program. In secondary analyses, implementation outcomes over a 6-month and 18month period will be assessed and described. We will examine how implementation outcomes change over time using descriptive methods (e.g. plots, descriptive statistics, subgroups). Descriptive statistics for survey measures such as organizational readiness for implementation change will be calculated overall and by randomization arm. We will use the same modeling approach described above to examine the effect of the implementation strategy on survey measures. To address the question: What is the impact on effectiveness outcomes/quality metrics (quality of VA General Caregiver Program, Veteran days in the community) at implementing sites? We will assess the impact of Caregivers FIRST on Veteran days in the

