Caregivers FIRST sample size estimate. Sample size calculations were conducted for the penetration implementation outcomes at 12-months. Based on a two-sided t-test based on a sample size of 25 sites (12 foundational REP and 13 higher intensity), a type-1 error rate of 5%, we will have 80% power to detect an effect size difference of 1.2 and 90% power to detect an effect size difference of 1.4 between arms. We did not adjust alpha for co-primary outcomes as success will be assessed based on improvement in both measurements of penetration. Analyses. To address the question: Are there differences in implementation outcomes (penetration, fidelity) at 6, 12, or 18 months between arms? We hypothesize that sites randomized to higher intensity strategies will achieve higher penetration and fidelity. As part of our type III effectiveness-implementation hybrid design framework, the primary research question compares differences in implementation outcomes (penetration, fidelity, and adoption) between implementation arms at 12 months. Implementation outcomes are continuous, count, and binary outcomes, and generalized linear models⁷⁵ will be used to examine the effect of high-touch support on implementation outcomes at 12 months. We will use generalized linear models⁷⁵ to examine the effect of implementation arm on implementation outcomes at 12months. The main predictor of interest will be enhanced (high touch) implementation support vs. foundational (low touch) implementation support, and stratification variables for site complexity (low complexity (2, 3, and no complexity) versus all others) and prior implementation of Caregivers FIRST or not will be included; other facility level covariates for consideration are CSP program quality score and size of CSP program. In secondary analyses, implementation outcomes over a 6-month and 18-month period will be assessed and described.. We will examine how implementation outcomes change over time using descriptive methods (e.g. plots, descriptive statistics, subgroups). Descriptive statistics for survey measures such as organizational readiness for implementation change will be calculated overall and by randomization arm. We will use the same modeling approach described above to examine the effect of the implementation strategy on survey measures. To address the guestion: What is the impact on effectiveness outcomes/quality metrics (quality of VA General Caregiver Program, Veteran days in the community) at implementing sites? We will assess the impact of Caregivers FIRST on Veteran days in the community (home time) over a 6-month period. Our sample of Veterans for this analysis will come from sites that adopt Caregivers FIRST nationally (that is, not limited to the 25 enrolled sites). The sample of Veterans will be from those whose caregiver received consults for VA caregiver education and training services, including to Caregivers FIRST over a year period after the program was announced as a minimum standard; some of those caregivers will attend Caregivers FIRST classes (i.e., treatment group) and some will not (i.e., comparison group). We will use inverse-probability of treatment weighted methods to adjust for confounding and estimate an average causal treatment effect for Caregivers FIRST on home time over the 6-month time period following the consult for a VA caregiver education

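### Caregivers FIRST: class activity in the 6-month run-in should be a prespecified covariate for the classes-delivered co-primary, because the FY21/FY22 stratum may not capture it

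*Combined protocol and SAP*

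**What the plan says.** All references are to Implementation Project 3: Caregivers FIRST unless stated.

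- **Eligibility** (Study design and methods). After six months of foundational REP, a site qualifies if it "did not deliver a round of Caregivers FIRST in first 6-months or had low enrollment defined as 4 or less caregivers trained" in that time.
- **Order of approach** (same section). Candidate sites are prioritized partly by "implementation activity (e.g., no implementation versus implementing but with low enrollment"), and within each VISN they are chosen "based on complexity level and lowest implementation activity within a VISN". The plan thus recognizes two kinds of non-adopting site.
- **Stratification** (same section). The factors are complexity and "prior implementation of Caregivers FIRST (implementation in FY21 or FY22 vs. none").
- **Outcome** (Outcomes). Penetration has two co-primary measures. The second is "the number of classes delivered over a 12-month period".
- **Model** (Analyses, repeated under Data Analysis and Statistical Considerations). Generalized linear models contain arm and both strata: "prior implementation of Caregivers FIRST or not will be included". Beyond these, "other facility level covariates for consideration are CSP program quality score and size of CSP program".
- **Success rule** (Sample size estimate). Both penetration measures must improve, with 12 versus 13 sites.
- **Clock** (Implementation Projects, Overview). Primary outcomes fall "between 10-18 months from the beginning of foundational REP".

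**The concern.** A round is four classes and two rounds per six months are recommended, so a site that failed only on caregiver numbers could have delivered four or even eight classes in the run-in. A site that qualified through having no program delivered none. The second co-primary counts classes, not caregivers, so these sites may differ widely in expected count before any extra support begins.

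No measure of run-in activity appears in the model. If such activity predicts later class delivery, and the FY21/FY22 indicator does not already stand in for it, the difference between the two kinds of site stays in the residual. With 25 sites, and success requiring improvement on both co-primaries, avoidable noise in one lowers the chance of a clear answer.

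The start of the 12-month count is also unstated. If it runs from the beginning of foundational REP, classes delivered before randomization are part of the outcome.

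**Working it through.** **1. The plan's own power.** Two-sided t-test, 12 versus 13 sites, alpha 0.05, 23 df. √(1/12 + 1/13) = 0.400, so the noncentrality is 1.2/0.400 = 3.00 and 1.4/0.400 = 3.50. Power is 81.9% and 91.7%. The detectable effects are 1.17 SD (80%) and 1.36 SD (90%). The stated 1.2 and 1.4 reproduce.

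**2. What the existing stratum captures.** The eligibility criterion is defined on a 6-month run-in. The stratifier is defined on fiscal years. No section dates the run-in, so the two may coincide, overlap or be separate. Even if they coincide, a yes/no stratum cannot distinguish one round from two.

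**3. Size of the precision effect.** The documents give neither the share of sites already running classes (q), nor their run-in counts (x), nor the number of later classes predicted by each run-in class (c), nor the residual SD. Assume residual SD 4 (variance 16) and a stratum unrelated to x. Then:

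- If x is 4 or 8 with equal chance at running sites and 0 elsewhere, Var(x) = 40q − 36q².
- If x is 4 at running sites, Var(x) = 16q(1 − q).
- Adding x multiplies the standard error by √(16/(16 + c²Var(x))), times about 1.02 for the extra covariate (the upper end of the penalty seen in simulation).

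| q | x if running | c | c²Var(x) | Ratio | × 1.02 | Simulated change |
|---|---|---|---|---|---|---|
| 20% | 4 or 8 | 1 | 6.56 | 0.842 | 0.859 | −14% |
| 40% | 4 or 8 | 1 | 10.24 | 0.781 | 0.797 | −20% |
| 20% | 4 or 8 | 0.5 | 1.64 | 0.952 | 0.971 | −2% |
| 40% | 4 or 8 | 0.5 | 2.56 | 0.928 | 0.947 | −5% |
| 20% | 4 | 1 | 2.56 | 0.928 | 0.947 | −5% |
| 40% | 4 | 1 | 3.84 | 0.898 | 0.916 | −8% |
| 20% | 4 | 0.5 | 0.64 | 0.981 | 1.000 | +0.6% |
| 20% | 4 or 8 | 2 | 26.24 | 0.615 | 0.628 | −37% |
| 40% | 4 or 8 | 2 | 40.96 | 0.530 | 0.541 | −46% |

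The value c = 2 means that the six-month pace continues for twelve months. The simulations used ordinary least squares with arm, complexity and the FY stratum.

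For x of 4 or 8 and c = 1, the simulated gain falls to 10–15% if the stratum agrees with run-in activity at 80% of sites, and to 0–2% if it agrees at all of them. With c = 0.5 and full agreement, the standard error rises by 1–2%.

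**4. The same effect as power.** Let ρ be the partial correlation of run-in activity with the outcome, given the strata. The residual SD is multiplied by √(1 − ρ²).

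| Model | 80%-power detectable effect (SD) | Power at 1.0 SD |
|---|---|---|
| Planned (21 df) | 1.18 | 66.4% |
| Added covariate (20 df), ρ = 0 | 1.18 | 66.2% |
| ρ = 0.3 | 1.13 | 70.2% |
| ρ = 0.5 | 1.02 | 78.3% |
| ρ = 0.7 | 0.84 | 91.4% |

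Counting only the lost degree of freedom, break-even is at ρ of about 0.07. Using the 2% penalty instead, it is √(1 − 1/1.02²) = 0.20, so these power gains are slightly optimistic.

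**5. Typical chance imbalance.** For x of 4 or 8 and c = 1, the SD of the difference between arms that is due to run-in classes is √6.56 × 0.400 = 1.0 class at q = 20%, and √10.24 × 0.400 = 1.3 classes at q = 40%.

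**6. The clock.** Month 12 from the start of foundational REP includes six run-in months. Twelve months from randomization is about month 6 + 12 = 18, the top of the Overview's range. The text fits either reading.

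**The case against.** The strongest reply is that earlier activity is already handled. Prior implementation is in both the randomization and the model, and if FY21/FY22 covers the run-in, little or nothing is left to gain. Approaching the least active sites first also thins out the running group. An eight-class site would have run two full rounds yet trained at most four caregivers, against a target of 10–12 per round. The calculations are for a linear model, while the plan allows count models. Finally, eligibility needs only whether a round was delivered and how many caregivers were trained, so exact class counts may not be held for every site.

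Much of this stands. The gain cannot be promised, and the larger figures need favorable assumptions. What does not follow is that the stratum is enough: nothing in the documents links it to the run-in, and the selection order does not exclude low-enrollment sites.

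Three stronger readings are tempting, and the documents do not support them:

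- A reader might infer that the plan ignores earlier activity. It does not; the FY stratum is used twice.
- A reader might infer bias or an inflated type I error from the mixed eligibility. Eligibility is fixed before randomization, so only precision is affected.
- A reader might infer that chance imbalance routinely shifts the result by several classes. With one-for-one carry-over, step 5 gives about one class. An imbalance of 25 percentage points in running sites gives 0.25 × 6 = 1.5 classes, and about 3 only if the run-in pace is sustained.

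**Conclusion.** The point holds as a matter of precision. The trial mixes sites with no classes and sites with some, counts classes as a co-primary, and adjusts for earlier activity only through a yes/no fiscal-year stratum of unknown relation to the run-in.

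The change in standard error from adding run-in classes runs from about +2% (weak carry-over, or a stratum that already captures run-in activity) to about −20% (20–40% of sites running four or eight classes, one-for-one carry-over, unrelated stratum). It is larger if the run-in pace continues. Every figure in that range rests on assumed values.

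The case for acting is the asymmetry between a small, bounded cost and a possibly material gain at 25 sites. It does not extend to the first co-primary. That outcome is a proportion of consulted caregivers, and nothing available shows that a run-in caregiver count would help there.

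**What to change.** In the Caregivers FIRST Analyses paragraph and its counterpart under Data Analysis and Statistical Considerations, add before outcomes are analyzed:

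*The 12-month model for classes delivered will also adjust for implementation activity in the 6-month foundational run-in, entered as the number of classes delivered or, if exact counts are not held for all sites, as none versus some.*

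- State how the run-in dates relate to FY21 and FY22. If the covariate and the stratum coincide at every site, the covariate cannot be estimated separately and should be left out; say so in advance.
- Under Outcomes, state that the 12-month count starts at randomization, and align the Overview with this.
- Leave the randomization strata as they are. Changing one partway would put two schemes into a 25-site trial.
- Add no caregiver-count covariate for the first co-primary.

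The cost is a sentence or two of text and one degree of freedom, worth up to about 2% in standard error if run-in activity predicts nothing. Whether extra data retrieval is needed depends on what class records exist for the run-in; the none-versus-some form should need little beyond what site selection already uses.

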
Implementation Evaluation. We will use mixed-method designs for two distinct but complementary purposes in the overall evaluation of each project. We describe our mixed-method approaches here, as we will use similar techniques across all projects. Data sources will include 1) EHR data accessed through CDW and JLV; 2) implementation process data such as site-reported EBP adaptations, and field and call notes including polls (e.g., Webex or Poll Everywhere); and 3) quantitative surveys and semi-structured interviews completed twice, in the: a) pre-implementation phase at baseline; and b) post-implementation phase, which is 10-18 months post-implementation depending on the EBP (Fig. 3).

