community (home time) over a 6-month period. Our sample of Veterans for this analysis will come from sites that adopt Caregivers FIRST nationally (that is, not limited to the 25 enrolled sites). The sample of Veterans (approximately 20,000) will be from those whose caregiver received consults for VA caregiver education and training services, including to Caregivers FIRST over a year period after the program was announced as a minimum standard; some of those caregivers will attend Caregivers FIRST classes (i.e., treatment group) and some will not (i.e., comparison group). Data sources include CDW, VA/CMS repository data, Caregiver Support Program Data, and Geriatrics and Extended Care Data Analysis Center (GECDAC) Residential History File data. We will use inverse-probability of treatment weighted methods to adjust for confounding and estimate an average causal treatment effect for Caregivers FIRST on home time over the 6-month time period following the consult for a VA caregiver education and training. We use the same modeling approach described above to examine the effect of implementation approach on general program quality scores and size of the general caregiver program. In exploratory analysis, we are interested in assessing the impact of Caregivers FIRST on Veteran's days in the community over a 6-month period. Our sample of Veterans for this analysis will come from sites that adopt Caregivers FIRST. The sample of Veterans will be from those whose caregiver received consults for VA caregiver education and training services, including to Caregivers FIRST over a year period; some of those caregivers will attend Caregivers FIRST classes (i.e. treatment group) and some will not (i.e. comparison group). We will use inverse-probability of treatment weighted methods to adjust for confounding and estimate an average causal treatment effect for Caregivers FIRST on home time over the 6month time period following the consult for a VA caregiver education and training. The study team will determine a priori which covariates are likely to be key determinants of attending Caregivers FIRST training. We will explore the distribution that best fits the days at home outcome: Poisson, Negative Binomial, or zero-inflated. Generalized linear models with inverse propensity score weights will be used. We will describe the quality metrics using descriptive statistics, but these will not be modeled. Qualitative data collection and approaches to data integration have been described previously. To address the key questions: What are the costs for delivering one round of Caregivers FIRST training? What are the costs of the high- and lowintensity implementation support? The business case will include a budget impact analysis to help VA administrators consider the cost of implementation and delivery along with the effectiveness of the intervention in the context of the VA priorities to improve Veteran outcomes. The budget impact analysis will evaluate implementation costs for each strategy and intervention delivery costs per participant. The high-touch implementation support strategy is expected to use more resources (delivery time and attendance time) and potentially improve implementation outcomes, for example improved fidelity or increased penetration. To assess the value of the additional investment in implementation support, we will describe implementation costs per enrolled participant for each implementation strategy. While the overall resource use might be higher, a lower cost per participant would indicate a high value. We will use staff time and equipment data from the adaptations survey (baseline, 6 months, and 12 months) to assess costs using U.S. Veterans Health Administration salary and managerial cost accounting data. Drawing from methods in prior Function QUERI work, Business Case Analysis (BCA) will frame affordability to VA. For the cumulative 12-month study period, two types of costs will be collected for each site using a standardized method to track implementation activities 1) clinical delivery team costs incurred and 2) implementation strategy costs incurred. Because the 25 sites enrolled will represent a fraction of the sites nationally who will also implement (expect over 100 to implement), we can extrapolate to a national scenario in the BCA.

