
Sample size estimate. Sample size calculations were conducted for the penetration implementation outcomes at 12-months. Based on a two-sided t-test based on a sample size of 25 sites (12 foundational REP and 13 higher intensity), a type-1 error rate of 5%, we will have 80% power to detect an effect size difference of 1.2 and 90% power to detect an effect size

difference of 1.4 between arms. We did not adjust alpha for co-primary outcomes as success will be assessed based on improvement in both measurements of penetration **Leadership**. [name] [name], health economist and health services researcher, evaluates delivery and costs of long-term services and supports, including interventions to support informal caregivers. She is the director of the QUERI Partnered Evaluation of the nationwide VA Caregiver Support Program (VA CARES) and the Function and Independence Scientific Core at the Durham COIN ADAPT.

Rapid Response Team

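### Caregivers FIRST: the arm model for survey measures does not use the baseline survey score, and program size and quality are undated candidate covariates as well as outcomes of arm

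*Combined protocol and SAP*

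**What the plan says.** All references are to the combined protocol and SAP. The text is in Implementation Project 3: Caregivers FIRST, Analyses, and most of it is repeated under Data Analysis and Statistical Considerations.

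- **Primary model.** Implementation outcomes at 12 months are analysed by generalized linear models with arm and two strata (site complexity, prior implementation). The plan adds: "other facility level covariates for consideration are CSP program quality score and size of CSP program". It gives no measurement date and no rule for inclusion.
- **Surveys.** "We will use the same modeling approach described above to examine the effect of the implementation strategy on survey measures". Under Implementation Evaluation, the data sources include "quantitative surveys and semi-structured interviews completed twice", once before implementation and once after.
- **Program size and quality as outcomes.** The same approach is used to "examine the effect of implementation approach on general program quality scores and size of the general caregiver program".
- **A contrary sentence.** Later in the same section the plan says that quality metrics will be described and not modelled. Specific Aim 2 lists the number of enrolled caregivers among the quality metrics.
- **Power.** "Sample size calculations were conducted for the penetration implementation outcomes at 12-months". No power is stated for survey measures, program size or program quality.

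**The concern.** There are two separate issues.

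**Surveys.** A baseline score is scheduled, but the model carried over to the surveys does not name it. With 12 and 13 sites per arm, chance baseline differences can be sizeable, and site-level survey scores may well correlate over time. Leaving the baseline out gives up precision that the trial can ill afford.

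**Program size and quality.** These may adjust the co-primary penetration models, and they are also analysed as outcomes of arm. Nothing in the text separates the two roles by time. If values measured after randomisation entered the co-primary models, part of any effect acting through program size or quality would be adjusted away. The open choice of whether to include them also leaves room for a decision influenced by the results.

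**Working it through.** **1. The plan's own power figure.** Inputs: "two-sided t-test based on a sample size of 25 sites (12 foundational REP and 13 higher intensity"; two-sided alpha 0.05. Power = 1 − F(t₀.₉₇₅,df; df, δ), where F is the noncentral t distribution function and δ = d / √(1/12 + 1/13) = d / 0.400.

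- With df = 23, d = 1.2 gives 81.9% and d = 1.4 gives 91.7%.
- The detectable d is 1.17 at 80% power and 1.36 at 90%.
- This reproduces "80% power to detect an effect size difference of 1.2 and 90% power to detect an effect size difference of 1.4 between arms". The figure concerns penetration and is not in dispute.

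**2. Chance imbalance without a baseline term.** The difference in baseline means between arms has SD √(1/12 + 1/13) = 0.400 site-level SDs. The chance that it exceeds 0.5 SD in either direction is 2[1 − Φ(0.5/0.400)], about 21%.

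**3. Adding the site's baseline mean.** The model with arm and two strata has 25 − 4 = 21 residual df; adding baseline leaves 20. With baseline to follow-up correlation r between site means, δ = d / √[(1 − r²)(1/12 + 1/13)]. The documents give no value of r, so the values below are assumptions. Detectable differences are in SDs of the site mean.

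| Model | Detectable d, 80% power | Change from 1.176 |
|---|---|---|
| No baseline, 21 df | 1.176 | reference |
| Baseline, r = 0, 20 df | 1.179 | +0.3% |
| Baseline, r = 0.4 | 1.179 × √0.84 = 1.081 | −8% |
| Baseline, r = 0.5 | 1.021 | −13% |
| Baseline, r = 0.6 | 0.943 | −20% |
| Baseline, r = 0.7 | 0.842 | −28% |

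If the baseline proved uninformative, the loss would be negligible.

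**4. A covariate measured after randomisation.** Suppose arm shifts the covariate by a SD and the covariate has slope b on the outcome. With a true total effect of 1.2 SD, the adjusted estimate targets 1.2 − ab. Simulation with 12 and 13 sites, 5,000 runs per setting, agrees:

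| a | b | 1.2 − ab | Simulated, post-randomisation value | Simulated, pre-randomisation value |
|---|---|---|---|---|
| 0.4 | 0.3 | 1.08 | 1.08 | 1.20 |
| 0.4 | 0.5 | 1.00 | 1.01 | 1.21 |
| 0.8 | 0.3 | 0.96 | 0.95 | 1.19 |
| 0.8 | 0.5 | 0.80 | 0.80 | 1.20 |

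The values of a and b are assumptions. The table shows what would follow if post-randomisation values were used; it does not predict that they will be.

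**The case against.** The case for leaving the plan alone has several parts.

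- **The covariates look like baseline characteristics.** They are described as facility-level and stand beside two pre-randomisation strata. Elsewhere the project dates site characteristics to earlier fiscal years. This is a fair reading, so the bias is only conditional. It does not supply the missing date or inclusion rule.
- **The size and quality models inherit their own baselines.** A reader might infer that these models leave out the baseline of the same measure. The documents do not support that: the inherited approach lists program size and quality as candidate covariates, and values dated before randomisation would be those baselines. What is missing is the date and the commitment. Read literally, an undated covariate could put the same measure on both sides of the model.
- **No effect on size or quality is predicted.** A reader might infer that the plan expects the arm to change them. The hypothesis covers penetration and fidelity only; for size and quality the plan poses a question.
- **Survey clustering.** Leaders and team members are surveyed, so a reader might infer that several respondents per site will be analysed as independent, with inflated type I error. The documents do not propose that. The model carried over was written for site-level outcomes, so site-level survey values are its natural reading.
- **Survey stakes are modest.** Surveys are not among the listed Caregivers FIRST outcomes, and the Implementation Core section treats them mainly as support for the qualitative work. This stands. The 1.2 SD used to plan penetration should also not be read as a survey target, so the survey gain is given here only as a relative change in detectable difference.

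**Conclusion.** The point holds as two wording gaps of different reach.

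The survey model leaves out a scheduled baseline. The consequence is lost precision and unadjusted chance imbalance, with no bias on average. The gain from adding it is about 8% to 28% in detectable difference at 80% power, resting on assumed correlations of 0.4 to 0.7 and on a usable baseline mean from every site.

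The dual role of program size and quality reaches the co-primary models, but the harm is conditional. A reader might infer that the co-primary estimate is already biased; the text does not show that, because it never says post-randomisation values will be used. This part also assumes that the covariates and the outcomes are the same measures. Their names differ slightly (caregiver support program against its general caregiver program), and neither is defined.

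Whether size and quality are modelled outcomes at all is unclear, because one sentence models them and a later one says quality metrics are only described.

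**What to change.** 1. **Surveys.** For each measure taken at both waves, analyse the follow-up site mean with arm, the two strata and the site's baseline mean. State that the baseline wave precedes randomisation and how a site with no baseline response is handled.
2. **Co-primary models.** Allow program quality score and program size only as values fixed before randomisation, with a named date and source. Decide whether they enter before any outcome is seen by arm.
3. **Size and quality as outcomes.** Where either is modelled, include its own pre-randomisation value. Say whether these are the same measures as the candidate covariates.
4. **Reconcile** the modelling sentence with the statement that quality metrics are described only, listing which measures fall under each.
5. Make the same edits in both places where the analysis text appears.

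The cost is a few sentences and one degree of freedom per survey, size or quality model. The baseline survey wave is already scheduled. Pre-randomisation program size and quality scores would have to be confirmed as available, since the documents do not specify their collection.
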